## 19 Statistical Methodology

The Sponsor will be responsible for the overall analysis of data from this CIP. The Statistical Analysis Plan (SAP) will describe all planned analyses based on the statistical design of this study and the subsequent data collected. A brief statistical overview of key statistical analyses is provided below.

### 19.1 Levels of Significance

Significance levels and the type-I error will be controlled for the primary and secondary endpoints at a one-sided 2.5% level.

## 19.2 Sample Size Justification

CCI [REDACTED]

CCI [REDACTED]

CCI [REDACTED]

### Total Sample size:

The sample size of this study is mainly driven by the hypothesis test for the primary safety endpoint. The total sample size for this study will be 135 evaluable subjects, CCI [REDACTED]

A total of 135 evaluable subjects will be included in the main study. Each of the four (4) subsets (NA, CT/MRA, EE and PVI durability) will target 30 subjects and will be integrated within the main study. Additionally, 30-50 subjects will be evaluable in the roll-in phase. CCI [REDACTED]

## 19.3 Analysis Sets

Safety Population Analysis Set (SP): CCI [REDACTED]

Modified Intention-To-Treat (mITT) Analysis Set: CCI [REDACTED]

Per Protocol (PP) Analysis Set: CCI [REDACTED]

CCI [REDACTED]

CCI [REDACTED]

**Roll-in Analysis Set:** CCI [REDACTED]

**Neurological Assessment (NA) Analysis Set:** CCI [REDACTED]

**Esophageal Endoscopy (EE) Analysis Set:** CCI [REDACTED]

**Cardiac CT/MRA Analysis Set:** CCI [REDACTED]

**PVI Durability Analysis Set:** CCI [REDACTED]

#### 19.4 General Conventions

Standard descriptive summaries for continuous data include the number of observations with data, mean, standard deviation, median, 25% percentile, 75% percentile, minimum, and maximum values. For categorical data, the count and percent will be provided. Percentages will be based on the number of subjects without missing data.

#### 19.5 Subject Disposition

Disposition and accountability of the study subjects will be summarized descriptively for the subject categories defined as following,

**Enrolled Subjects:** Patients who sign the ICF.

**Excluded Subjects:** Subjects who are enrolled but never undergo insertion of the study catheter. Excluded subjects will be subjected to safety event reporting between ICF signature and date of exclusion. Subjects who signed the ICF but are found to be ineligible prior to insertion of the catheter are also considered as excluded.

**Evaluable Subjects:** All enrolled subjects who have the study catheter inserted.

**Discontinued Subjects:** Evaluable subjects who have the catheter inserted, but do not undergo ablation (i.e., no energy is delivered with the study catheter).

- Discontinued subjects will remain in follow-up for 3- months post catheter insertion.
- Discontinued subset subjects are not subjected to the additional subset assessments (esophageal, neurological, PV and PVI durability).
- If an SAE is reported for a discontinued subject, the subject will be followed until event resolution (with or without sequelae), stabilization, or until the event is adequately explained.

**Lost to Follow-up Subjects:** Evaluable subjects of which contact is lost after most recent visit (despite 3 documented attempts to contact the subject and a final documented attempt (e.g., certified letter).

**Withdrawn / Early Termination Subjects:** Subjects who withdraw consent for study participation or are withdrawn by the investigator, are terminated from the study prior to completion of all follow-up visits.

**Completed Subjects:** Enrolled subjects who have not been excluded, discontinued, withdrawn, terminated early, or lost-to-follow-up from the study prior to the final study visit.

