11.5.4 System Components and Setup

11.5.4.1 Required Study Devices

To conduct an electrophysiology procedure, the OMNYPULSE™ Bi-Directional Catheter and TRUPULSE™ Generator are used with the following Biosense Webster non-CE marked devices. Table 2 displays the devices which must be used for the ablation procedure and are required per CIP.

Table 2: Required Study Devices

Non - CE marked Devices	Function
OMNYPULSE™ Bi-Directional Catheter	Transmits energy to the target tissue.
TRUPULSE™ Generator	Delivers PF energy to compatible ablation catheter
Sterile Catheter Interface Cable	Connects the OMNYPULSE™ Bi-Directional Catheter with the TRUPULSE™ Generator.
Compatible Guiding Sheath	Facilitate deployment of the OMNYPULSE™ Bi-Directional Catheter into the atria.
CE Marked BWI Devices	Function
CARTO™ 3 SYSTEM V7.9 workstation	For mapping and visualization information with software for PF
nGEN™ Pump	Delivers heparinized saline to the catheter

SMARTABLATE™ Irrigation Tubing Sets (SAT001)	Delivers heparinized saline to the catheter
Patient Interface Unit (PIU) of the CARTO™ 3 system	The EP recording system should be connected to the CARTO 3 System PIU to transfer ECG
BWI multi-electrode mapping catheter	
 
• Pre-ablation recording and mapping of the atria of the heart with the CARTO™ 3 System.
 
• Confirmation of entrance block
 

Tx Eco Cable	Connector between the OMNYPULSE™ catheter and the system (CIU/PIU) for information of location and contact force.

The following devices, CE marked by other companies, are also required for the procedure:

- Electrophysiology (EP) Recording System
- Stimulator
- Body Surface Electrocardiogram (ECG) Patches and Leads
- Indifferent electrode patch(es)
- Fluoroscopy/X-Ray System
- Cardiac Defibrillator
- Intracardiac Ultrasound (Investigator preference, not required)
- Esophageal Temperature Monitoring Device (OPTIONAL)

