- **Imaging (TTE or other acceptable equivalent cardiac imaging – i.e., CT/MRA) within 6 months prior to procedure to assess the LA and LVEF.** Must be collected within 6 months prior to procedure, in case of the imaging assessment is older than 6 months LA/LVEF, dimensions shall be re-measured during the index ablation procedure prior to insertion of the study catheter. In case of re-measurements before study catheter insertion fail to meet the LA and/or LVEF criteria, the subject will be considered as not meeting eligibility and will be excluded.
- Imaging for **detection of left atrial thrombus** or other structural contraindications to an ablation procedure is mandatory the day before or on the day of the ablation procedure. Presence of a thrombus will require postponement of the ablation procedure or may even lead to exclusion of the subject from further study involvement. The imaging method to be used for atrial thrombus detection is TEE, Intracardiac Echocardiography (ICE), Cardiac CT or MRI
- **Electrocardiogram** (12-Lead ECG). Data from 12-lead ECG recordings will be collected.
- **Adverse Events** must be collected from the time the subject signs the informed consent onwards.
- Quality of life via the **Atrial Fibrillation Effect on Quality-of-Life (AFEQT™)** questionnaire (non-Standard of Care). NOTE: Patient questionnaires will only be used in countries with validated languages.
- **Cardiac CT/MRA** is required to be performed for all subjects within 6 months prior to the ablation procedure to assess the structure and size of the PVs and the left atrial anatomy.
- Additional Assessments for **NA subset** subjects: **Cerebral MRI, Neurological Exam and Neurological Evaluation using the MMSE, NIHSS and mRS (non-SOC)** are required to be performed within 72-hours pre-procedure (for procedures on Monday a window of a maximum of 96 hours is justified) to evaluate the neurological condition and presence of neurological deficits of the subjects before undergoing study ablation procedure. A certified/qualified physician expert must perform neurologic exams at pre-and post-ablation and possibly at other follow-up visits, pending previous findings of micro-emboli/neurologic deficits. Pre-and post-ablation cerebral MRIs will be analyzed by a central core lab to determine the frequency, size, and anatomical location of cerebral micro-emboli, if any. NOTE: Patient questionnaires will only be used in countries with validated languages.

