  - ACT must be targeted to be maintained  $\geq 350$  seconds throughout the ablation.
  - ACT level must be checked on regular basis while investigational device is in the left atrium.
  - If ACT is below 350 seconds, systematic anticoagulation with heparin should be administrated to ensure an ACT target of 350 seconds without pausing ablation procedure.
- Introduction of the compatible 10 F guiding sheath, if not used for mapping. Before inserting the sheath into the patient, flush the sheath with heparinized normal saline to remove air bubbles.
- Introduce the investigational OMNYPULSE™ Bi-Directional Catheter as per IFU.
- **NOTE:** Usage of a diagnostic catheter or any metal device in the same chamber during ablation is strictly prohibited, and diagnostic catheter should be disconnected from the CARTO™ 3 system prior to starting ablation.
- When position is satisfactory, commence energy delivery with the investigational catheter per recommended workflow.
- **NOTE:** In the situation that the CARTO™ system shuts down, the connection configuration will not allow the OMNYPULSE™ catheter to pace. An alternative method (e.g., CS catheter) must be in place in order to pace in case of emergency.

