### **Ablation outside the PV region**

- **A right atrial CTI linear** ablation is allowed only in cases with documented typical atrial flutter identified either prior to or during the procedure. The CTI line should be completed with a BWI commercially approved and compatible (RF) catheter and (RF) generator.
- **Prophylactic ablation** outside the PV region (in example SVC, PW, roofline) is NOT allowed.
- If an arrhythmia is requiring ablations outside the PV:
  - **Prior** to insertion of the study catheter (consistent with exclusion criteria) investigators will be required to switch to the commercial setup using a commercially available Biosense Webster catheter used with a commercially available RF generator. The subject will be considered a screen failure (<ICF signature) or excluded from the study (> ICF signature).
  - **After insertion of** the study catheter, the subject will undergo PVI with study set up followed by ablation with a commercially approved BWI (RF) catheter and compatible RF generator to complete the procedure for the treatment of arrhythmia outside PV region. The subject will be evaluable for acute success and followed till 3-months post procedure. NOTE: Ongoing AE(s) at 3 months shall be followed up until resolution (with or without sequelae)

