**Table 5: Primary Adverse Events**

Primary Adverse Event	Description / Criteria
Death 	Subject death directly related to the device or procedure and occurs at any time during or after the procedure.
Atrio-Esophageal Fistula 	Defined as a connection between the atrium and the lumen of the esophagus. Evidence supporting this diagnosis includes documentation of esophagus erosion combined with evidence of a fistulous connection to the atrium such as air emboli, an embolic event, or direct observation at the time of surgical repair. A CT or MRI scan is the most common method of documentation of an AEF.
Myocardial Infarction	
Presence of any one of the following criteria:
 
 
- Detection of ECG changes indicative of new ischemia (new ST-T changes or new Left Bundle Branch Block [LBBB]) that persist for more than 1 hour.
 
- Development of new pathological Q waves on ECG
 
- Imaging evidence of new loss of viable myocardium or new regional wall motion abnormality
 

Cardiac Tamponade  /Perforation	
The development of a significant pericardial effusion during or within 30 days of undergoing the index AF ablation procedure. A significant pericardial effusion is one that results in hemodynamic compromise, requires elective or urgent pericardiocentesis, or results in a 1 cm or more pericardial effusion as documented by echocardiography.
 
Cardiac tamponade/perforation should also be classified as:
 
 
• Early – diagnosed prior to discharge.
 
• Late – following initial discharge from the hospital.
 
 
Cardiac Tamponade/Perforation occurring within 30 days of the index ablation procedure will be considered a PAE for the study.

Thromboembolism	
Formation of a clot (thrombus) inside a blood vessel causing obstruction to blood flow accompanied by clinical symptoms. The thrombus can migrate (embolus) and obstruct distal vascular sites.
 
Diagnostic tests to help detect thromboembolisms may include but are not limited to angiography (pulmonary or distal), ventilation-perfusion (V/Q) scans, venography, Doppler ultrasonography, spiral CT, and echocardiography.
 
For the purpose of this study silent (asymptomatic) cerebral embolism will not be considered a PAE.

Primary Adverse Event	Description / Criteria

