### 14.4 Reporting Procedures

#### 14.4.1 Adverse Event Documentation and Reporting Requirements

Subjects should be encouraged to report AEs spontaneously or in response to general, non-directed questioning (e.g., "How was your health been since last visit?"). Anytime during the study, the subject may volunteer information that resembles an AE.

Each AE must be reported to the sponsor regardless of classification, seriousness, intensity, outcome or causality. The investigator is responsible for ensuring that all AEs observed by the investigator, or reported by the subject, that occur from the time that the subject has signed the informed consent through the end of the study are properly assessed, recorded, and reported as defined and described in the AEs, Adverse Device Effects and Device Deficiencies section of this CIP (section 14). All AEs must be documented by completing subject's medical records (source documents) and appropriate eCRF by the investigator or study coordinator throughout the study and provided to the Sponsor. All AEs will be monitored until they are adequately resolved or explained.

Anonymized documentation pertaining to the AE (e.g., laboratory tests, consultation reports, post-mortem reports, new information relating to a previously reported AE, correspondence with the local EC, etc.) will be provided by the investigator to the sponsor or designee in a timely manner, when requested. Follow-up reports relative to the subject's subsequent course must be submitted to the sponsor or designee until the event has resolved or, in case of permanent impairment, until the condition stabilizes. If the subject is withdrawn from the study because of the AE, the information must be included on the appropriate eCRFs.

The Sponsor is responsible for the classification of AEs and ongoing safety evaluation of the study and shall review the investigator’s assessment of all AEs. The sponsor will determine and document in writing their seriousness and relationship to the investigational device. In case of disagreement between the sponsor and the PIs, the sponsor shall communicate both opinions to the concerned parties.

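### Protocol 19.5 ends safety reporting on the exclusion date even when exclusion follows transseptal puncture or sheath insertion, and this is not reconciled with the AE rules in 14.3 and 14.4.1

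*Protocol*

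**What the plan says.** Protocol 19.5 defines excluded subjects as "Subjects who are enrolled but never undergo insertion of the study catheter" and adds: "Excluded subjects will be subjected to safety event reporting between ICF signature and date of exclusion". SAP 7.2 takes over these disposition categories unchanged. The next category in 19.5, discontinued subjects (catheter inserted, no energy delivered), stays in follow-up for 3 months, and any SAE is followed until it is resolved, stable or explained.

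The general rules are wider. Section 14.4.1 makes the investigator responsible for all AEs "that occur from the time that the subject has signed the informed consent through the end of the study", with no exception for excluded subjects. Section 14.3 has AEs followed to resolution, stabilisation or adequate explanation.

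On exposure before the catheter goes in, 13.3.3 lists transseptal puncture under preparation, ahead of mapping. The ablation steps then include "Introduction of the compatible 10 F guiding sheath, if not used for mapping". Table 2 puts the guiding sheath in its non-CE-marked block and gives its function as "Facilitate deployment of the OMNYPULSE™ Bi-Directional Catheter into the atria".

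On exclusion during the procedure, 13.3.3 says that if an arrhythmia needs ablation outside the pulmonary veins and the study catheter is not yet in, "investigators will be required to switch to the commercial setup"; a subject who has already consented is then excluded. Section 13.2.1 adds that when LA/LVEF imaging is out of date and re-measurements at the index procedure "fail to meet the LA and/or LVEF criteria, the subject will be considered as not meeting eligibility and will be excluded".

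**The concern.** The line between full safety follow-up and none is drawn at one device, the study catheter. It is not drawn at invasive exposure, nor at exposure to any investigational device. Yet the objective in section 6.1 evaluates the catheter together with the guiding sheath, and the sheath is not CE-marked.

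Perforation, tamponade and access bleeding can arise from puncture or sheath handling without any pulsed-field energy. Table 5 recognises that tamponade can appear late: its definition is "The development of a significant pericardial effusion during or within 30 days of undergoing the index AF ablation procedure", with a separate class for cases found after discharge. If 19.5 governs, the window for a subject excluded mid-procedure closes on the date of exclusion, presumably the procedure day. What is at stake is complete safety data on an investigational accessory in a pre-market study whose 3-month report goes into the CE-mark dossier.

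**Working it through.** The plan states no figure on this point, so the check sets its rules side by side and then bounds the size.

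**1. Safety window by how far the procedure went**

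| State when the subject leaves the study treatment path | Category in 19.5 | Stated safety window |
|---|---|---|
| Consent only, no access | Excluded | Consent to exclusion date |
| Access and transseptal puncture, possibly sheath; no study catheter | Excluded | Consent to exclusion date |
| Study catheter in, no energy | Discontinued | 3 months; SAEs to resolution |
| Study catheter in, PVI done, non-PV ablation also needed | Evaluable | 3 months (13.3.3) |
| Study catheter used as planned | Evaluable | 12 months |

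The second row is the problem: it has the same window as a subject who was never touched.

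**2. Can the second row occur?** In 13.3.3, puncture comes before mapping. Mapping with the study catheter is recommended, but a multi-electrode mapping catheter or 3D rotational angiography may replace it. So the septum can be crossed before the study catheter is inserted. The sheath is listed before the catheter and may already be in from mapping. The non-PV arrhythmia route to exclusion covers the whole time before catheter insertion, including this interval. The LA/LVEF route might also fall here, but nothing says that re-measurement follows vascular access.

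**3. Which reporting rule applies?** Section 14.4.1 can be read in two ways.
- If end of study means the study end in section 25 (last visit of the last subject, or the last 12-month assessment), 14.4.1 requires what 19.5 switches off, and the two conflict.
- If it means the end of that subject's participation, the conflict goes, but so does any duty to collect an event with onset after exclusion.

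On either reading no visit or call is scheduled. Section 14.3 has the investigator ask about AEs at study visits, which an excluded subject no longer has. A later event would reach the sponsor only if the subject volunteered it or the investigator happened to see it.

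**4. Size.** Inputs: the number *k* of subjects excluded after invasive access is not given, so assume 1 to 5, with 10 as an extreme. Table 9 gives cardiac tamponade 0.2% to 5% and vascular complications 0.2% to 1.5%.

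Expected events = *k* × (tamponade rate + vascular rate)
- Lowest: 1 × (0.002 + 0.002) = 0.004
- *k* = 5, highest rates: 5 × (0.05 + 0.015) = 0.325
- *k* = 10, highest rates: 10 × 0.065 = 0.65

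These figures overstate what would be missed. They include events on the day of exclusion, which 19.5 does cover, and the rates are for complete AF ablation procedures rather than puncture or sheath alone.

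**5. Primary safety test.** Evaluable subjects in 19.5 are those with the study catheter inserted, so excluded subjects lie outside the 135. With n = 135, a goal of 12% and the exact one-sided 2.5% test, the trial passes with at most 8 events: 8/135 = 5.9%, upper bound 11.34%, P(X ≤ 8 | 0.12) = 0.0146. Nine events fail, with upper bound 12.28%. An unrecorded event in an excluded subject does not enter this count.

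**The case against.** The case against is substantial, and much of it stands.

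- A reader might infer that these subjects lose all safety follow-up and that a late event is never recorded. The documents do not support that. Events with onset by the exclusion date fall inside the 19.5 window and are followed under 14.3, and 14.4.1 read literally covers later ones. The supportable statement is that the rules are unreconciled and no contact is planned.
- A reader might also infer that such events appear in no table. That cannot be checked, because the Safety and mITT set definitions are redacted in both documents.
- Sheath exposure without the study catheter is inferred. Table 2 ties the sheath to deploying that catheter, and prior use for mapping may simply mean mapping with the study catheter, in which case the subject is evaluable. Exposure through transseptal puncture alone does not depend on this inference.
- The LA/LVEF route should be rare. It needs imaging older than 6 months, yet every subject must have a cardiac CT/MRA within 6 months, and 13.2.1 accepts CT/MRA as equivalent imaging.
- Section 7.4.1 defines the primary endpoint for procedures in which the investigational catheter and generator are used, so the 7-day and 30-day windows do not formally apply here. They show only how late the plan expects such events to appear. Commercial RF ablation after exclusion would also make attribution to the sheath difficult.

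Studies may reasonably limit follow-up to subjects who received the study device. That does not answer the point, because the guiding sheath is also under evaluation and 14.4.1 makes no exception.

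**Conclusion.** The concern holds as a gap in the completeness of safety data. Section 19.5 closes reporting at exclusion whatever the subject has already undergone, 14.4.1 and 14.3 do not clearly override it, and no contact is scheduled that would find a delayed tamponade or access complication. It does not show that such harm would certainly go unrecorded.

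The size is probably very small: well under one expected event on every assumption above, and lower still once same-day events are removed. This rests on an assumed 1 to 5 (at most 10) subjects and on the incidence ranges in Table 9. The primary test is unaffected, provided that the redacted mITT set contains only subjects with the study catheter inserted, as the evaluable category implies. The point merits a targeted wording change because the study is pre-market, a single serious case would matter, and sites cannot tell which rule to follow.

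**What to change.** Reconcile 19.5 with 14.3 and 14.4.1 for subjects excluded after vascular or transseptal access, or after any investigational device including the guiding sheath has entered the body. Restrict the exclusion-date cut-off to subjects with no such exposure. For the exposed subjects, the sponsor should state the safety reporting window and how events will be sought within it. The choice of window is a clinical matter for the sponsor, and none is proposed here.

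In the SAP, list the adverse events of these subjects separately, with their number and the reason for exclusion. Leave the effectiveness and primary safety denominators unchanged.

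The cost is protocol and SAP wording, a few extra contacts, and possibly one or two more reported events. Some of these may be hard to attribute where commercial ablation followed.
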